Procedure. The study will use a randomized wait-list controlled design. The parent (mother or father) primarily involved in their child’s daily T1DM management will be invited to participate with their child. We will plan to recruit 24 families to each of the immediate treatment and wait-list control groups (we will target at least 20 families per group to complete the study; 20% attrition rate). A member of the research team will identify families eligible to participate. Parents will undergo randomization after they provide written informed consent. We will stratify parents based on their child’s gender and conduct random assignment to the two groups using blocks of four. We intend to recruit three family cohorts each consisting of 16 families (8, immediate treatment, 8 wait-list). We will instruct parents randomized to the wait-list control group to follow their physician’s recommendations for their child’s T1DM. Then, after the 14 week wait-list control period, we will invite parents in the control group to participate in RED CHiP. We will instruct parents randomized to the immediate treatment group to follow their physician’s recommendations for their child’s T1DM. In addition, they will receive 14 weeks of RED CHiP. Parents randomized to the immediate treatment group will also complete a follow up assessment, corresponding with the time when parents in the wait-list control group have finished the RED CHiP program (see Figure 2). Because we plan to use a mixed-method approach to evaluate the feasibility and acceptability of RED CHiP, we will also randomly sample 5 parents from both the immediate treatment and wait-list control groups (n=10 total) to complete a semi-structured qualitative interview. Parents will complete the interview at the time of their last assessment visit (e.g., followup, for parents in the immediate treatment group; post-treatment for parents in the wait-list control group). Parents will be able to complete all of the surveys online either with their own computer or an iPad 2 loaned to them by the study. A research assistant will work with parents to complete the online surveys, download children’s glucometers and insulin pump, and collect a finger stick blood sample to measure children’s Hemoglobin A1c (HbA1c) at each time point.

Figure 2. Intervention Timeline

[figure not shown]

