
Orientation. A trained research assistant will conduct orientation visits following randomization for families in the immediate treatment group and the wait-list period for families in the wait-list control group. These visits will include training on how to use the iPad and *Real Presence m500 app*.

Accelerometer. During RED CHiP, children will wear an accelerometer (Actigraph GT3X) for at least 5 days to measure their typical daily physical activity (PA). In young children, the link between glycemic response and PA remains unclear. Accelerometer data will provide an accurate measure of children's PA, since research shows that parents often underreport their child's engagement in unstructured PA.⁴¹ Children's total daily PA (total movement counts/total measurement time in minutes) will be calculated as well as a diagram of their typical daily PA patterns. We will use these data to educate parents regarding the relationship between their child's activity patterns and blood glucose levels. We expect that giving parents specific strategies for insulin dosing and carbohydrate intake in the context of their child's typical PA routine will improve parents' T1DM management and children's glycemic control.

Wait-list Control. After randomization, families assigned to the wait-list control condition will receive a copy of the clinics' standard flow sheet for the treatment of hypoglycemia. Families will cross over to the treatment arm at the end of the 14-week wait-list period.

Outcome Measures. Primary outcome measures will be: parents' FH, parenting stress, children's glycemic levels (measured using mean daily blood glucose levels and HbA1c), and children's glycemic variability (measured using the average daily risk range and the low blood glucose index). Secondary outcome measures will be the Feasibility and Acceptability of RED CHiP. Covariates for these pilot analyses will be parents' depressive symptoms and child age (see Table 3). If more than one parent participates in RED CHiP, we will use the data from the parent who self-identifies as the most responsible for their child's T1DM management in the study analyses. If parents indicate equal responsibility, we will collect data from both parents for each time point and we will average both parents' data for the analyses.

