Data Management and Statistical Analyses. Parents will input their data into a RedCap database accessible via the internet. Missing data for continuous variables that cannot be recovered from parents will be imputed using either subscale or total scale mean score substitutions (e.g., HFS-PYC, PIP, CES-D). Again, covariates for Hypotheses 2a-b and 3a-b will be parents' depressive symptoms (DS), and child age (AGE).

Hypotheses.

Hypothesis 1: RED CHiP will be feasible and acceptable to families of young children with T1DM.

Hypothesis 2a and b: Parents who receive RED ChiP will have a reduction in fear of hypoglycemia (HFS-PYC) and parenting stress (PIP) as compared to the wait-list group (*Hyp 2a*) and pre-RED ChiP measures (*Hyp 2b*).

Hypothesis 3: Children whose parents receive RED ChiP will experience an improvement in mean glycemic levels (MDBG & HbA1c) and variability (ADRR & LBG1) as compared to the wait-list group (*Hyp 3a*) and pre-RED ChiP measures (*Hyp 3b*).

Power analysis. This is a pilot and feasibility study with the purpose of generating data to support a full, randomized controlled trial. Power analysis of a test of the difference between pre- and post-HFS-PYC with a 10% decline in survey scores (i.e., from $M=78.6 \pm 18.4^{17}$ to $M=71$) yielded a power of 84%, while a 15% decline in PIP-F scores (i.e., from a $M=107.2 \pm 32.6^{27}$ to $M=91$) yielded a power of 92% when $n=40$, $\alpha=0.05$ for both tests. Repeated measures ANCOVA (RM-ANCOVA via GLM) yielded a power of 92% and 82%, respectively, for 10% declines in parents' HFS-PYC and PIP-F scores. When using RM-ANCOVA and assuming a 10% decline in children's HbA1c, tests yielded 95% power when $n=40$ and $\alpha=0.05$ ($M=8.8 \pm 1.5\%$ to 8.0%). Assuming an attrition rate of 20%, we will need to recruit 48 parents (24 per group) to ensure we have ≥ 40 parents with post-treatment data. This sample size is also sufficient to estimate effect sizes for the study outcomes.

Data Analysis. We will first run descriptive statistics and statistical distributions for all measured variables at baseline (B), weeks 15-16 (w15-16), and weeks 32-33 (w32-33). We will conduct sensitivity analyses for all primary outcomes to evaluate any effects due to attrition. We will also use an intent-to-treat analysis strategy, wherein we will use an imputation model to examine participant data even if they are lost to attrition.

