	Average Daily Risk Range (ADRR)	A measure of risk of glycemic variability; ⁵¹ scores are calculated based on a minimum of 14-days of self-monitoring blood glucose (SMBG) data; scores >40 suggest a high risk for variability; has been used previously in young children; ³⁵ our pilot data show a correlation between children's ADRR scores and percent of low blood glucose values ($r=0.93$, $p=0.03$)
	Low Blood Glucose Index (LBGI)	A measure of risk for a low blood glucose level; ⁴⁵ based on a normalized transformation of SMBG to remove bias due to the natural asymmetry of blood glucose (greater range of hyper versus hypoglycemic levels); LBGI is based on a minimum of 14-days of data; sensitive to hypoglycemic events only; our pilot data show a correlation between children's LBGI and percent of low blood glucose values ($r=0.88$, $p<0.001$)
SECONDARY MEASURES:	Feasibility (Quantitative)	Feasibility of RED ChiP will be based on attendance to group sessions $\geq 70\%$ and attrition $\leq 25\%$
	Acceptability (Quantitative)	Acceptability of RED ChiP will be based on our Treatment Satisfaction Questionnaire, a 16-item measure; the Treatment Satisfaction Questionnaire will use a 5-point Likert scale to assess perceived acceptability of the RED ChiP content and structure (mean score ≥ 65 , range: 16-80)
COVARIATES:	Demographic & Medical History	Family/child characteristics; medical history; T1DM events; we will collect this during the baseline assessment; child age will be used as a covariate
	Center for Epidemiologic Studies-Depression Scale (CES-D)	20-item self-report; ⁴⁷ reliable in parents of children with T1DM; ²⁹ superior to Beck Depression Inventory in identifying depressive symptoms in T1DM; ^{46,48-49} Total Score will be used as a covariate; higher values suggesting greater frequency of depressive symptoms

Note. Please see Appendix A for sample questions from each measure.

Hypotheses 2a and b: We will score outcome measures as continuous variables with within-group standardized effect sizes (in SD units) and within-group changes for FH (HFS-PYC) and parenting stress (PIP-F and PIP-D) calculated based on parents' B, w15-16, and w32-33 scores. To test for between-group differences on parents' FH and stress at B, w15-16, and w32-33, we will use both repeated measures ANCOVA (RM-ANCOVA) and a 2x2 factorial (condition x time) MANCOVA. We will also use these to test for *within-group x time* differences. Our covariates will be AGE and DS.

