Hypotheses 3a and b: We will calculate within-group standardized effect sizes (in SD units) and within-group changes for children's glycemic levels and variability based on children's B, w15-16, and w32-33 values. As in Hypothesis 2, we will employ General Linear Models (GLMs) such as RM-ANCOVA and a 2x2 factorial (condition x time) MANCOVA to test for between-group differences on children's glycemic levels (MDBG & HbA1c) and variability (ADRR & LBGI) at B, w15-16, and w32-33 and for *within-group x time* differences. Our covariates will be AGE and DS.

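### The between-group tests for Hypotheses 2a and 3a include weeks 32-33, when the wait-list arm has also finished RED CHiP, and no deciding contrast is named

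*Combined protocol and SAP*

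**What the plan says.** All references are to the combined protocol and SAP.

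- **Hypotheses:** 2a (fear of hypoglycemia, parenting stress) and 3a (glycemic levels and variability) are each stated "as compared to the wait-list group". 2b and 3b compare with measures taken before RED CHiP.
- **Wait-list Control:** "Families will cross over to the treatment arm at the end of the 14-week wait-list period".
- **Procedure:** the immediate-treatment parents "complete a follow up assessment, corresponding with the time when parents in the wait-list control group have finished the RED CHiP program".
- **Hypotheses 2a and b:** to test between-group differences on "FH and stress at B, w15-16, and w32-33, we will use both repeated measures ANCOVA (RM-ANCOVA) and a 2x2 factorial (condition x time) MANCOVA". The covariates are child age (AGE) and parental depressive symptoms (DS).
- **Hypotheses 3a and b:** the same two models test between-group differences in levels and "variability (ADRR & LBGI) at B, w15-16, and w32-33".
- **Power analysis:** RM-ANCOVA "yielded a power of 92% and 82%, respectively, for 10% declines" in HFS-PYC and PIP-F. The model term is not identified.

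**The concern.** The wait-list arm is untreated only up to weeks 15-16. By weeks 32-33 both arms have had RED CHiP, one recently and one some months before, so a between-arm difference there contrasts immediate with delayed treatment. The plan puts that visit into the between-group tests for hypotheses about treatment versus wait-list.

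The 2x2 label does not settle the matter. It implies two times where three are listed, does not say which two, and does not restrict the RM-ANCOVA. With two models and no deciding term, the answer to 2a/3a could depend on a choice made after the data are seen. These are the trial's primary outcomes, and the pilot is meant to support a full randomised trial.

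**Working it through.** **The plan's own figures.** A one-sided paired t test at 0.05 with n = 40, taking the SD of change equal to the stated SD, gives:

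- HFS-PYC, 7.86/18.4: 84.4% (stated 84%)
- PIP-F, 16.08/32.6: 92.2% (stated 92%)

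These are pre-post tests. A two-sided two-sample test of HFS-PYC at 20 per arm has only about 26%. For the RM-ANCOVA figure of 92% for HFS-PYC, a two-sided within-person test on 40 would need a correlation of about 0.69, and a between-arm change test at 20 per arm about 0.92. The stated power therefore does not reveal a between-group deciding term.

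**Inputs from the plan.** Effects in SD units:

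- HFS-PYC, 10% decline: 7.86/18.4 = 0.427
- PIP-F, 10% decline: 10.72/32.6 = 0.329
- HbA1c, 8.8 to 8.0: 0.8/1.5 = 0.533

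**Assumptions not in the plan.** 20 completers per arm, two-sided 5%, equal SDs, equal between-visit correlation ρ from 0.5 to 0.8, AGE and DS ignored.

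**Expected arm difference (baseline, w15-16, w32-33).** With effect d, the same and lasting in both arms, it is (0, d, 0).

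**Power by deciding term.** The standardised effects below are multiplied by √(20/2) and referred to a noncentral t on about 38 df:

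- Group effect over three visits: (d/3)/√((1+2ρ)/3)
- Change, baseline to w15-16: d/√(2(1−ρ))
- w15-16 adjusted for baseline: d/√(1−ρ²)

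Example, HFS-PYC at ρ = 0.5: the group effect is 0.142/0.816 = 0.174, noncentrality 0.55, power 8.4%. The change is 0.427/1 = 0.427, noncentrality 1.35, power 26.1%.

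| Outcome | Three-visit group effect | Change to w15-16 | w15-16 adjusted for baseline |
|---|---|---|---|
| HFS-PYC | about 8% | 26-55% | 33-59% |
| PIP-F | about 7% | 17-36% | 22-39% |
| HbA1c | 9-10% | 38-74% | 48-78% |

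A simulation of the baseline-adjusted HFS-PYC test (20,000 replicates) gave about 32% and 58% at ρ = 0.5 and 0.8, in line with the table. In points, the three-visit group effect estimates 7.86/3 = 2.62. Averaging only the two post-baseline visits, adjusted for baseline, estimates 7.86/2 = 3.93, with about 15-25% power.

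**Three-visit condition-by-time test** (HFS-PYC, F on 2 and 76 df, noncentrality 10·Σ(difference − mean difference)²/(1−ρ) in SD units):

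| Pattern of arm difference | Power, ρ = 0.5 to 0.8 |
|---|---|
| Lasting (0, d, 0) | 26-57% |
| Half fades in the immediate arm (0, d, −d/2) | 42-83% |
| All fades (0, d, −d) | 66-97% |
| Immediate arm gains a further d/2 (0, d, d/2) | 20-45% |

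Under no effect the simulated rejection rate was 5.0% and 5.1%, so error control is intact. But significance becomes more likely as benefit is lost and less likely as it grows, so the test does not by itself answer 2a/3a.

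**Separate tests by visit.** The w15-16 test is unaffected. At w32-33 the expected difference is zero if effects last. If half fades it is 0.5 × 7.86 = 3.93 points (0.21 SD) in favour of the wait-list arm.

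**The case against.** The strongest reply is that the near-null result needs the least natural reading, a group effect averaged over all visits including baseline. The text more readily suggests visit-by-visit or condition-by-time tests. The first leaves w15-16 intact; the second keeps its type I error and, if effects last, matches the change test for power (26-57% against 26-55%). The 2x2 model may well mean baseline and w15-16. The paragraphs also serve 2b/3b, which need w32-33. The only effect sizes the plan specifies are within-group, so the diluted estimate would not enter them. Finally, this is a pilot, the fading scenarios are hypothetical, and low power comes mainly from 20 per arm.

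Much of this stands. The dilution is conditional on one reading, and w32-33 has a proper use under 2b/3b. Using the rounded HFS-PYC means (78.6 to 71, a 7.6-point decline) changes little: the change test has 25-52%.

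It does not remove the problem. The plan attaches w32-33 to between-group differences in so many words, and the 2x2 label neither names its visits nor governs the RM-ANCOVA. If only within-group effect sizes are specified, the treatment-versus-wait-list estimate is tied to no visit at all.

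**Conclusion.** The concern holds and should be fixed. A three-visit RM-ANCOVA run as written includes a visit without an untreated control. Depending on the term reported, it either dilutes the effect to a third (HFS-PYC 2.62 instead of 7.86 points, about 8% power instead of 26-55%) or does not isolate treatment versus wait-list. Separate visit tests would preserve w15-16, but nothing says that visit decides.

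The power figures rest on the assumptions listed above, and the dilution also on equal, lasting benefit in both arms. The figure showing the timeline is not available; that w32-33 is the follow-up described under Procedure is inferred from the two 14-week periods and its place as the last assessment. The corrected test remains modestly powered; naming it secures interpretation, not adequate power.

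**What to change.** State that 2a and 3a are each decided, for each outcome, by one named test. Preferably this is the condition effect at w15-16 adjusted for the baseline value of that outcome, plus the planned AGE and DS. The alternative is the 2x2 condition-by-time test restricted to baseline and w15-16. Report the matching between-arm estimate with its confidence interval as the effect size for planning the full trial.

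Use w32-33 for the wait-list arm's own change from w15-16 under 2b/3b and for maintenance in the immediate arm. Label any between-arm contrast at w32-33, or any three-visit interaction, as a secondary comparison of immediate with delayed treatment. In the Power analysis, say which term the RM-ANCOVA figures refer to.

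The cost is SAP wording only. It needs no new visits or data, and the w32-33 comparison is kept.

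### The between-group tests for 2a and 3a use baseline only as a level of time; adjusting the w15-16 value for its own baseline would add modest precision at almost no cost

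*Combined protocol and SAP*

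**What the plan says.** The section Data Management and Statistical Analyses states that "covariates for Hypotheses 2a-b and 3a-b will be parents' depressive symptoms (DS), and child age (AGE"). Outcome Measures names the same two covariates, and the analysis paragraphs for Hypotheses 2 and 3 each close with "Our covariates will be AGE and DS".

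The baseline outcome appears only as time point B. For Hypothesis 2: "To test for between-group differences on parents' FH and stress at B, w15-16, and w32-33, we will use both repeated measures ANCOVA (RM-ANCOVA"), together with a 2x2 condition x time MANCOVA. For Hypothesis 3 the plan will "employ General Linear Models (GLMs) such as RM-ANCOVA and a 2x2 factorial (condition x time) MANCOVA". The words 'such as' leave that list open, but no section adds the baseline outcome as a covariate.

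Under Wait-list Control, "Families will cross over to the treatment arm at the end of the 14-week wait-list period". Power analysis calls the study a pilot meant to support a full trial and adds: "This sample size is also sufficient to estimate effect sizes for the study outcomes".

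**The concern.** Hypotheses 2a and 3a ask whether families given RED CHiP do better than wait-listed families. Only w15-16 can answer this, because by w32-33 both arms have been offered the programme. The plan lists three time points and does not single that contrast out.

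Taking B and w15-16 as the two levels of time in the 2x2 model, the condition x time term compares mean change between arms. A change score fixes the slope on baseline at 1, whereas ANCOVA estimates it. When r is well below 1, fixing the slope adds noise to the comparison. In a study with about 20 completers per arm, whose purpose is to inform a larger trial, that means a wider interval than the collected data allow. Bias is not at issue.

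**Working it through.** **Inputs from the documents.** There are 20 completers per arm (Procedure). Power analysis gives HFS-PYC 78.6 to 71, SD 18.4 (difference 7.6); PIP-F mean 107.2, SD 32.6, with a 10% decline for RM-ANCOVA (10.72); HbA1c 8.8 to 8.0, SD 1.5 (difference 0.8); and α = 0.05, sidedness not stated.

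**Assumptions.** r is not given, so a range is shown. The between-arm difference equals the stated decline, meaning no change in the wait-list arm. Tests are two-sided, data are normal, and AGE and DS are estimated in both models but have no effect.

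**The plan's own figures.** The pre-post powers of 84% (HFS-PYC) and 92% (PIP-F, 15% decline) are reproduced by a one-sided paired t-test with n = 40 and SD of change equal to the stated SD, which corresponds to r = 0.5. Using the exact declines of 7.86 and 16.08, this gives 84.4% and 92.2%. Two-sided tests give 75.0% and 86.0%.

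**Step 1: the planned test is a change-score test.** In a simulated data set with 20 per arm, a repeated-measures fit with subject effects and covariate-by-time terms gave a condition x time estimate of -0.482 (t = -1.389). Regressing w15-16 minus B on arm, AGE and DS gave the same estimate and the same t.

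**Step 2: closed form, with equal SDs at both times.**

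- SE(change) = SD·√(2(1−r))·√(2/20)
- SE(ANCOVA) = SD·√(1−r²)·√(2/20)
- Variance ratio = (1−r²)/(2(1−r)) = (1+r)/2

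For HFS-PYC at r = 0.5: 18.4 × √1 × √0.1 = 5.82 and 18.4 × √0.75 × √0.1 = 5.04, a fall of 13.4%. At r = 0.6, 0.7, 0.8 and 0.9 the falls are 10.6%, 7.8%, 5.1% and 2.5%. These are slightly optimistic because they ignore the cost of estimating the slope.

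**Step 3: simulation with that cost included** (40,000 trials per cell; residual df 36 for change, 35 for ANCOVA).

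| r | HFS-PYC SE, change → ANCOVA | SE fall | Equivalent change-score n per arm | HFS-PYC power | PIP-F power | HbA1c power |
|---|---|---|---|---|---|---|
| 0.5 | 5.94 → 5.22 | 12% | 25.9 | 24% → 29% | 17% → 20% | 36% → 44% |
| 0.6 | 5.31 → 4.82 | 9% | 24.3 | 28% → 33% | 19% → 23% | 43% → 50% |
| 0.7 | 4.60 → 4.30 | 6% | 22.9 | 36% → 40% | 25% → 27% | 54% → 60% |
| 0.8 | 3.76 → 3.62 | 4% | 21.6 | 50% → 53% | 34% → 37% | 71% → 75% |
| 0.9 | 2.66 → 2.63 | 1% | 20.5 | 79% → 80% | 60% → 61% | 95% → 95% |

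Equivalent n is 20 × (SE change / SE ANCOVA)²; at r = 0.5, 20 × (5.94/5.22)² = 25.9. The 95% half-width for HFS-PYC goes from 12.0 to 10.6 points at r = 0.5, 7.6 to 7.3 at 0.8, and 5.4 to 5.3 at 0.9. The SE gain is 0.1% at r = 0.94 and turns into a loss of 0.1% at 0.95. Type I error was 5.0–5.2% for both tests. If DS is assumed to correlate 0.4 with the outcome at both times, the SE falls are 15.0%, 4.8% and 1.7% at r = 0.5, 0.8 and 0.9.

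**Step 4: what r do the plan's powers imply?** Read as two-sided paired tests with n = 40, all five stated powers imply r of 0.58–0.75. Read as between-group change tests with 20 per arm, the three RM-ANCOVA powers (92%, 82%, 95%) imply 0.90–0.94. Allowing one-sided tests and exact rather than rounded declines widens these ranges to about 0.39–0.75 and 0.85–0.94.

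**The case against.** The strongest reply is that nothing here is an error. The planned test is valid, the study is a pilot, and near r = 0.9 the two analyses are almost the same. All of that stands, and it makes this an optional improvement.

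The effect sizes that the analysis paragraphs promise are within-group, and the change leaves those untouched. That is true. But 2a and 3a are stated as between-group hypotheses, and the between-group difference is the quantity a later randomised trial needs.

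The plan can also be read differently. If testing differences at w15-16 means comparing the arms at that visit alone, the variance ratio becomes 1−r² (0.75 at r = 0.5, 0.51 at r = 0.7). The unadjusted SE for HFS-PYC is then about 5.9 at every r, so adjustment helps more as r rises. A condition effect averaged over all three time points would mix pre-treatment and post-crossover data and answer neither hypothesis. Both readings strengthen the case for naming the contrast.

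The inputs mix rounded means (7.6, 0.8) with an exact 10% (10.72), because the documents give no rounded PIP-F target for that decline. With the exact declines of 7.86 and 0.88, closed-form power at r = 0.5 is 26% → 33% for HFS-PYC and 44% → 55% for HbA1c. The size of the gain is similar.

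Separate ANCOVAs replace a joint MANCOVA for 2a and 3a. RM-ANCOVA is already planned alongside the MANCOVA, so outcome-by-outcome testing is not new.

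**Conclusion.** The concern holds as a point to consider. The plan does not adjust the between-group comparison for the baseline outcome, and the baseline to w15-16 condition x time test is a change-score contrast. Adjusting would cut the HFS-PYC standard error by 12% at r = 0.5, 4% at 0.8 and 1% at 0.9, worth about 6, 2 and 0.5 extra families per arm. Power would rise by at most about 8 percentage points across the three outcomes computed. For HFS-PYC and PIP-F it stays below 55% for r up to 0.8.

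The algebra is certain. The size depends on r, which the documents do not give, and on the assumption that the wait-list arm does not change. If the stated RM-ANCOVA powers were meant as between-group tests, r is high and there is little to gain.

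**What to change.** For 2a and 3a, prespecify one between-group contrast: an ANCOVA of the w15-16 value on arm, adjusted for the baseline value of that outcome, child age and baseline CES-D, reported as an adjusted difference with its 95% interval. The text does not say which visit's CES-D is meant; the baseline value keeps the covariate free of any treatment effect. Do not enter baseline as a covariate while also keeping B as an outcome level, since that is redundant.

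Keep the repeated-measures models for the within-group questions 2b and 3b. Child gender may be added to match the stratified randomisation, but no precision gain should be claimed for it: with no gender effect, it changed the mean SE by at most 0.2% and power by at most 0.4 points.

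The cost is SAP wording and one residual degree of freedom (36 to 35 with 40 families; two if gender is added). That cost is already in the simulated figures. It takes up about half of the SE gain at r = 0.9 (2.5% in closed form, 1.2% simulated) and all of it from about r = 0.94.

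### Randomisation is stratified by child gender but the outcome models omit it, so between-group tests at single time points are slightly conservative if gender is prognostic

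*Combined protocol and SAP*

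**What the plan says.** The Procedure section sets the allocation: "We will stratify parents based on their child’s gender and conduct random assignment to the two groups using blocks of four". It is 1:1, with 24 families planned per group.

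Covariates are stated four times, always the same two. Outcome Measures and the opening of Data Management and Statistical Analyses name parents' depressive symptoms and child age. The analysis paragraphs for Hypotheses 2a and b and for Hypotheses 3a and b each close with "Our covariates will be AGE and DS". Table 3 agrees.

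For between-group differences at baseline, weeks 15-16 and weeks 32-33, the Hypotheses 2a and b paragraph says "we will use both repeated measures ANCOVA (RM-ANCOVA) and a 2x2 factorial (condition x time) MANCOVA". The Hypotheses 3a and b paragraph plans the same models for the glycaemic outcomes. Gender enters no model, subgroup or sensitivity analysis, and no reason is given for leaving it out.

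**The concern.** The design treats gender as worth balancing and the analysis treats it as noise. Stratified blocks bring the gender mix of the two arms close together, so chance imbalance in gender contributes little to the variation of the group difference from one possible randomisation to another. A model without gender still counts the gender variance as residual error and computes a standard error as if that imbalance had been left to chance. If gender is prognostic, intervals are a little too wide and tests a little too conservative.

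What is at stake is precision. The trial aims to have about 20 families per arm complete, and the Power analysis paragraph gives estimating effect sizes as one use of the sample. There is also a prespecification benefit: if gender is named now, nobody has to choose between models with and without it after seeing results.

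**Working it through.** **Inputs from the documents.** Two groups, 1:1; 48 families recruited and 40 analysed; permuted blocks of four within gender; covariates AGE and DS; alpha 0.05. Sidedness is not stated; two-sided is assumed below. The effect used for power is the 10% decline in HFS-PYC: 7.86 / 18.4 = 0.43 SD.

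**The plan's own figure.** The plan gives no figure for the effect of omitting gender. Its power figure confirms the effect size: a paired t-test with n = 40 and d = 7.86/18.4 gives 84.4% one-sided, matching the stated 84% (two-sided it is 75.0%). That test is pre-post, so it does not bear directly on the between-group question.

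**Assumption.** R² is the share of outcome variance explained by gender. The documents give no value, so a range is shown.

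**Closed-form size.** With gender balanced but omitted, the reported standard error is too large by the factor k = 1/√(1 − R²). The actual two-sided size is P(|t| > k × t_crit), with the tail taken from the same t distribution as the critical value. For 38 df, t_crit = 2.024.

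| R² | k | k × t_crit | actual size |
|---|---|---|---|
| 0 | 1.000 | 2.024 | 5.0% |
| 0.02 | 1.010 | 2.045 | 4.8% |
| 0.05 | 1.026 | 2.077 | 4.5% |
| 0.10 | 1.054 | 2.134 | 3.9% |

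With 36 df (40 families less four parameters: intercept, group, AGE, DS) the sizes are the same to this precision. Referring the t critical value to a normal tail would give smaller sizes (4.1%, 3.8%, 3.3%), but that method gives 4.3% even at R² = 0, where the answer must be 5.0%.

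**Simulation of the design.** 48 families were randomised within gender in blocks of four and 40 analysed at one time point. The two covariates were assumed to explain 20% of variance. There were 12,000 runs for size and 6,000 for power at d = 0.43. Each cell reads without gender / with gender.

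| R² | mean SE (SD units) | type I error | power |
|---|---|---|---|
| 0 | 0.289 / 0.290 | 5.3% / 5.3% | 29.7% / 29.4% |
| 0.05 | 0.290 / 0.281 | 4.2% / 4.7% | 29.4% / 31.6% |
| 0.10 | 0.290 / 0.271 | 4.3% / 5.3% | 28.3% / 32.5% |
| 0.20 | 0.290 / 0.251 | 2.8% / 4.9% | 28.4% / 37.8% |

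Monte Carlo error is about 0.2 points on size (√(0.05 × 0.95 / 12,000) = 0.002) and 0.6 points on power (√(0.3 × 0.7 / 6,000) = 0.006). A separate simulation of 20,000 runs gave sizes without gender of 4.9%, 4.4% and 4.1% at R² = 0.02, 0.05 and 0.10, in line with the closed form. At R² = 0.20, which lies above the range used for the headline figures, the model SE of 0.290 compares with an actual sampling SD of 0.261.

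**Which tests are exposed.** A two-time-point simulation with a constant gender effect at R² = 0.20 gave:

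- Change contrast (condition x time): SE 0.282 without gender, 0.283 with; type I error 5.0% and 4.9%. A constant gender effect cancels in the difference.
- Group main effect, averaged over time: SE 0.283 without gender, 0.245 with; type I error 2.8% and 4.9%.

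These runs used a single outcome. The multivariate test was not simulated.

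**The case against.** Three arguments on the other side have force.

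1. Nothing in the documents shows that child gender predicts parental fear, parenting stress or any glycaemic measure. Zero is as consistent with the text as 10%, and at zero nothing is lost. This stands: the size of the effect is conditional.
2. The plan's models include a condition x time term, which tests whether change differs by arm, and a constant gender effect drops out of it. This also stands, and limits the scope. A reader might infer that every test under Hypotheses 2a and 3a is affected; the documents do not support that. The same paragraphs do, however, plan between-group comparisons at each assessment, and those are exposed.
3. This is a pilot, and an error of a few percent in a standard error, in the conservative direction, threatens no conclusion. This stands as an argument about severity. It is not a reason to keep the omission, since correcting it costs almost nothing.

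A reader might also infer that ignoring the stratification biases the treatment effect or makes false positives more likely. It does neither: balance on gender protects the estimate, and the error in the test is towards too few rejections. Nor is all the benefit of stratifying lost. The groups stay balanced; only the credit for that balance is missing from the reported precision.

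**Conclusion.** The omission is real and consistent across all four covariate statements. Its consequence is small and conditional. If gender explains 2-10% of outcome variance, an assumed range, the standard errors for between-group tests at single time points and for the group main effect are about 1-5% too large, and a nominal two-sided 5% test runs at about 4.8-3.9%. In the simulated design, power at d = 0.43 would rise by about 2 points at R² = 0.05 (29.4% to 31.6%) and 4 points at R² = 0.10 (28.3% to 32.5%). The effect is therefore slight unless gender explains roughly 10% or more of the variance. The condition x time test is untouched unless gender predicts change. This is a minor improvement, worth making because the possible gain exceeds the negligible cost; it does not threaten the plan's conclusions.

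**What to change.** In Outcome Measures, in the opening of Data Management and Statistical Analyses, and in the analysis paragraphs for Hypotheses 2a and b and Hypotheses 3a and b, state that the covariates are AGE, DS and child gender, the last as the randomisation stratification factor. Apply this to all RM-ANCOVA and MANCOVA models, and bring the covariate rows of Table 3 into line.

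Gender must be known before a family can be randomised, so no new data are needed. The cost is a short addition to the text and one degree of freedom: 36 to 35 in a single-time-point ANCOVA with 40 families. If gender explains nothing, the simulated standard error moves from 0.289 to 0.290 and power from 29.7% to 29.4%, which is within simulation error.
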